### **10.1.3 Financial Disclosure**

All described guidelines and procedures apply equally to investigators and sites enrolling in Parts 1, 2, 3 and 4 of this study. In accordance with the FDA regulation (21 CFR Part 54) on Financial Disclosure by Clinical Investigators, Molecular Templates is required to include in marketing applications to the FDA either:

- Certification of the absence of certain financial interests or arrangements of clinical investigators,

OR

- Disclosure of certain financial interests or arrangements of clinical investigators.

Molecular Templates will request a statement attesting to any such financial arrangements. Disclosure is required for those financial interests other than the Clinical Study Agreement for this study. A statement will be required from all investigators and sub-Investigators who participate in a clinical study (defined as those directly involved in the treatment or evaluation of research subjects). This includes the financial interests of spouses and dependent children of the investigators. Any changes to the disclosure statement must be submitted in writing to Molecular Templates.

### **10.1.4 Informed Consent Process**

- The investigator will not undertake any measures specifically required only for the clinical study until valid consent has been obtained. If local SoC procedures or tests were performed prior to signing of the ICF but are still within 35 days of initiation of dosing, unless otherwise specified (eg, LVEF), then those results/data can be used for the intended protocol screening procedure. If various parameters within a given procedure are missing from the SoC procedures, then only those missing parameters need to be collected.
- The investigator's IRB/IEC will review and approve the study protocol and subject ICF and any other materials the investigator prepares for recruitment of subjects (eg, advertisements, study information brochures). All investigator generated subject information and recruitment materials must also be provided to Molecular Templates and its agents for review and approval. The ICF will contain all the elements required by the ICH E6 Guideline for GCP and any additional elements required by local regulations.
- Before being enrolled, the principal investigator or one of his/her sub-investigators must explain orally and in writing the nature, duration, purpose of the study, and the action of the study drug in such a manner that the subject or legally authorized representative is aware of possible risks, inconveniences, or adverse effects that may occur. The ICF must be in a language that is understandable to the subject or legally authorized representative. The subject or legally authorized representative will have sufficient time to read the document

prior to being asked if there are any questions about the study procedures. A qualified and trained member of the study team must respond to these questions (eg, a study staff member who has been specifically trained on the protocol). Where required by local law, the person who informs the subject must be the investigator or another physician designated by the investigator. The subject should be informed that they may withdraw from the study at any time. The subject will receive all information that is required by the local regulatory authorities and ICH guidelines.

- The subject's consent must be confirmed at the time of consent by the personally dated signature of the subject. If the subject is unable to read, oral presentation and explanation of the written ICF and information to be supplied to subjects must take place in the presence of an impartial witness. Consent must be confirmed at the time of consent orally and by the personally dated signature of the subject or by a local legally recognized alternative (eg, the subject's thumbprint or mark). The witness to the informed consent discussions must also sign and personally date the ICF. A copy of the ICF must be given to the subject. The original signed ICF will be retained by the investigator.

### **10.1.5 Data Protection**

- Subject names will not be supplied to the sponsor. Only the subject number will be recorded in the electronic case report form (eCRF), and if the subject name or any other personal identifier appears on any other document (eg, pathologist report), it must be obliterated before a copy of the document is supplied to the sponsor.
- Study findings stored on a computer will be stored in accordance with local data protection laws.
- The subjects will be told that representatives of the sponsor, IRB/IEC, or regulatory authorities may inspect their medical records to verify the information collected, and that all personal information made available for inspection will be handled in strictest confidence and in accordance with local data protection laws.

### **10.1.6 Study Monitoring**

Contract research organization personnel may monitor the conduct of this study on behalf of the sponsor. Monitoring will include on-site visits, remote online access, and telephone communication to assure that the study is conducted according to the protocol and to assess the site's compliance with GCP guidelines and other regulations. On-site or online review of eCRFs will assess the completeness and clarity, and consistency with source documents available for each subject.

### **10.1.7 Source Documents**

#### **10.1.7.1 Case Report Forms and Study Records**

It is a regulatory obligation of the investigator to maintain adequate and accurate case histories (source documentation) designed to record all observations and data pertinent to the investigation for each subject. Source Documents are the documents where information regarding a subject is

first recorded. Investigator subject files or hospital records are generally the basis of source document information. All source documentation must be available during site visits for the assigned Monitor to review and compare with the completed eCRFs. The investigator must maintain source documents.

If the site is required to use a subject's medical / hospital record to submit to sponsor/CRO, all subject identifiers must be made invisible to maintain subject's anonymity and confidentiality.

For this trial Monitors will perform source document verification as per the monitoring plan. It is critical that all information contained in the eCRF can be corroborated by the Source Documents that are used. Source documents may include but are not limited to all original documents, data, and records (eg, hospital records, clinical and office charts, laboratory notes, memoranda, subjects' diaries or evaluation checklists, pharmacy dispensing records, recorded data from automated instruments, copies or transcriptions certified after verification as being accurate and complete, photographic negatives, microfilm or magnetic media, X-rays, subject files and records kept at the pharmacy, at the laboratories and at technical departments involved in the clinical study) that pertain to a study subject during the course of the clinical study. Source documents may also include past and current medical and medication history, documentation of informed consent (signed ICF, including all amendments as required by local authorities), subject study identification (eg, subject number, protocol number), ECOG assessments, International Working Group Criteria, documentation of dosing and study procedures/evaluations, all AE records and any protocol deviations.

All data will be collected on study specific eCRFs, with the exception of central laboratory data, which will be provided to the investigator on a laboratory report and submitted to the clinical database via electronic transfer from the testing laboratory. Local laboratory data will be entered into the case report form (CRFs) by trained and qualified study staff.

Monitors and auditors must have access to original records (unless copies are certified as authentic copies). Source data must be legible, written concurrently with the subject visit, and no data may be obliterated.

All potentially eligible and appropriately consented study candidates will be entered into the study's electronic data base with the initiation of screening. This information will be retained for all dosed subjects as well as subjects who fail 1 or more screen procedures or withdraw consent following screening and never progress to receive study drug.

For all enrolled subjects, eCRF pages will be completed for all study activities (eg, MT-3724 administration/dosing, safety assessments, procedures) These entries will be completed from the baseline visit forward until the end of the study (early termination or study completion) and combined with the screen entries be included in each subject's complete study documentation package.

All protocol-required information collected during the study must be entered by the investigator, or designated representative, in the eCRF. Details of eCRF completion and correction will be provided in the eCRF completion guidelines and will be explained to the investigative staff. If

the investigator authorizes other persons to make entries in the eCRF, the names, positions, signatures, and initials of these persons must be supplied to the sponsor/CRO.

The eCRFs must be reviewed by the principal investigator and signed by the principal investigator named in the clinical study protocol at the end of the study. Any changes to the eCRF after retrieval using data clarification forms or queries must also be authorized/signed by the principal investigator and/or the study coordinator and/or the data entry coordinator. (Note: Study Coordinators and Data Entry Coordinators are sometimes allowed to sign Data Clarification Forms.) The sponsor or CRO acting as an agent of the sponsor will retain the final, complete electronic data base with all eCRFs. The investigator will retain a copy of all eCRF pages completed at their site.

#### **10.1.7.2 Access to Source Documentation**

Domestic and foreign regulatory authorities, the IRB/IEC, and an auditor authorized by the sponsor may request access to all source documents, eCRF, and other study documentation for on-site audit or inspection. Direct access to these documents must be guaranteed by the investigator, who must provide support at all times for these activities. Medical records and other study documents may be copied during audit or inspection provided that subject names are obliterated on the copies to ensure confidentiality. If the investigator is informed of an impending regulatory authority audit, the sponsor must be notified within 24 hours of the investigator's notification by the inspecting authority.

#### **10.1.7.3 Retention of Data**

Study documents for all parts of this study must be retained until at least 5 years after the last marketing approval in an ICH region or at least 5 years have elapsed since the formal discontinuation of clinical development of the investigational product (eg, via notification of the FDA or local regulatory authority). The investigator/institution may not destroy records without written authorization from the sponsor. If an investigator leaves the institution at which the study was conducted, arrangements must be made to ensure another responsible party is designated to maintain the records.

Unless otherwise noted, all described guidelines and procedures apply equally to subjects enrolled in all parts of this study. The following records must be retained by the investigator/institution for a minimum of 2 years after the sponsor has notified the FDA that investigations have been discontinued or after the FDA has approved the new drug application:

- Signed ICFs for all subjects
- Subject identification code list, screening log (if applicable), and enrollment log
- Record of all communications between the investigator and the IRB
- Composition of the IRB or other applicable statement
- Record of all communications between the investigator and Molecular Templates and/or CRO

- List of sub-Investigators and other appropriately qualified persons to whom the investigator has delegated significant trial-related duties, together with their roles in the study and their signatures
- Copies of CRFs and of documentation of corrections for all subjects
- Drug accountability records
- Record of any body fluids or tissue samples retained
- All other source documents (subject records, hospital records, laboratory records, etc.)
- All other documents as listed in Section 8 of the ICH consolidated guideline on GCP (Essential Documents for the Conduct of a Clinical Trial)

Normally, these records will be held in the investigator's archives. If the investigator is unable to meet this obligation, he or she must ask the sponsor for permission to make alternative arrangements. Details of these arrangements must be documented in writing to the sponsor.

#### **10.1.8 Data Quality Assurance**

- Data will be recorded in an FDA CFR Part 11-compliant eCRF, also known as the electronic data capture (EDC) system.
- Data reported on the eCRF must accurately reflect the corresponding source documents, or the discrepancies must be explained. No data are to be recorded directly on the eCRFs (ie, the eCRF is not to be considered as source data).
- The investigator should agree to have completed source documents and eCRFs available for inspection by the Monitor on behalf of the sponsor at the time of each scheduled monitoring visit. The investigator must sign the completed eCRF for each subject after the study completion.
- All data obtained either from the eCRFs or from an external laboratory will be provided in descriptive summary tables presenting the number of subjects (n), mean, standard deviation, median, minimum and maximum for continuous variables and number of subjects (n) and percent for categorical variables.
- The sponsor or designee is responsible for the data management of this study including quality checking of the data. All clinical parameters should be entered into the eCRF /EDC as soon as possible after each study visit, preferably within 5 business days of the visit.

#### **10.1.9 Publication and Disclosure Policy**

All described guidelines and requirements apply equally to investigators and sites enrolling in all parts of this study. The information developed in the clinical study will be used by Molecular Templates in connection with the development of the investigational product. As such, the information may be disclosed to other investigators or regulatory authorities to obtain marketing approval. In order for Molecular Templates to use the clinical research information, the investigator is obligated to provide all of the information they obtain regarding the investigational product.

Compound: MT-3724

Protocol MT-3724\_NHL\_001

Protocol Date and Version: 12 February 2021, v11.0

Both Molecular Templates and the investigator are free to present or publish the results of the study. Any party proposing a publication will provide the other with a copy of the proposed publication for review and comment prior to the submission for publication. Manuscripts must be submitted 30 days in advance of submission and abstracts within 10 days. The sponsor must be acknowledged in all publications.

## 10.2 Appendix 2: Clinical Laboratory Tests

### 10.2.1 General Guidance

- The tests detailed in [Table 10-1](#) will be performed by the central laboratory or local laboratory as indicated. All screening laboratory tests must be collected within 28 days of start of treatment.
- The same laboratory should analyze all scheduled laboratory tests throughout the study.
- Local laboratory for chemistry and hematology should be collected to assess subject status / safety if results from central laboratory will not be available predose, whenever central laboratory assessments are scheduled. These results need only be entered in the electronic data capture (EDC) if there is a clinically significant (CS) finding, related to an AE except albumin and creatine phosphokinase (CK) collected during Cycle 1 which are collected locally and should be entered in the case report form (CRF) irrespective of clinical significance.
- For serial blood samples (PK analyses), an in-dwelling catheter (“hep lock”) placed in an extremity other than that used for MT-3724 infusion can be used to obtain the multiple blood samples stipulated in the protocol on dosing days.
- A standalone Laboratory Manual will provide complete instructions regarding how these samples should be collected, stored, and shipped.
- Additional tests may be performed at any time during the study as determined necessary by the investigator or required by local regulations.

**Table 10-1. Protocol-Required Laboratory Assessments**

Central Laboratory			Local Laboratory	
Hematology	Chemistry		Local Chemistry	
hematocrit	Albumin	eCrCl a	Albumin	CK e
hemoglobin	ALP	GGT	Urinalysis macroscopic a	
platelet count	ALT (SGPT)	glucose (fasting, plasma)	glucose	occult blood
RBC b	amylase	HbA1c	ketones	pH
WBC c	AST (SGOT)	LDH	leukocytes	protein
	β-HCG a	lipase	nitrites	specific gravity
	β-2 microglobulin	magnesium	Urinalysis microscopic (optional) a	
Coagulation	bicarbonate	phosphorous	bacteria	mucous threads
aPTT	bilirubin (total and direct)	potassium	casts	RBC
INR or PT	BUN	protein (total)	crystals	WBC
	calcium	sodium	epithelial cells	
Thyroid function	chloride	uric acid	Viral Serology (if applicable d )	
free T4	CK e		anti-HIV-1 antibody	anti-HBcAg antibody
TSH	creatinine		anti-HIV-2 antibody	HCV- RNA quantitation
Other Central Laboratory Analytes			HBsAg	anti-HCV antibody
anti-drug antibodies (ADA and NAb titer)			anti-HBsAg antibody	
			Virology (if applicable)	
			HIV viral load	

**Table 10-1. Protocol-Required Laboratory Assessments**

B-cell count and immunophenotype (flow cytometry) complement a cytokines (serum) a histamine a immunoglobulins (IgA, IgG, IgM) serum MT-3724 concentration (PK) CSF MT-3724 concentration (PK) serum rituximab concentration (if applicable) a	HBV viral load HCV viral load Other local laboratory tests CD4+ T-cell counts (if applicable) Pregnancy test (if applicable)
---	--

**NOTES:**

ADA = anti-drug antibody; ALP = alkaline phosphatase; ALT = alanine aminotransferase; aPTT = activated partial thromboplastin time; AST = aspartate aminotransferase; β-HCG = beta human chorionic gonadotropin; BUN = blood urea nitrogen; CK = creatinine phosphokinase; CSF = cerebrospinal fluid; eCrCl = estimated creatinine clearance; freeT4 = free thyroxin; GGT = gamma-glutamyl transferase; HBsAg = hepatitis B surface antigen; HbA1c = glycated hemoglobin; HBV = hepatitis B virus; HCV = hepatitis C virus; HIV = human immunodeficiency virus; Ig = immunoglobulin; INR = international normalized ratio; LDH = lactate dehydrogenase; NAb = neutralizing antibodies; PK = pharmacokinetic; PT = prothrombin time; RBC = red blood cell; SGOT = serum glutamic-oxaloacetic transaminase; SGPT = serum glutamic-pyruvic transaminase; TSH = thyroid-stimulating hormone; ULN = upper limit of normal; WBC = white blood cell.

a See [Section 10.2.2](#) for analyte-specific guidance.

b RBC indices (mean cell volume, mean corpuscular hemoglobin, mean corpuscular hemoglobin concentration) and distribution widths (red cell and platelet).

c WBC with differential (including neutrophils, basophils, eosinophils, lymphocytes, monocytes) reported as percentage and absolute values.

d The serology for individual virus(es) may be omitted at the investigator's discretion if seronegativity is documented in the medical history and there are no clinical signs of HIV or hepatitis infections, or suspected exposure.

e If CK is elevated > ULN, CK isoenzymes must be analyzed.

## 10.2.2 Analyte-specific Guidance

### 10.2.2.1 Pregnancy Test

Only applicable for women of childbearing potential. Women who are postmenopausal (> 1 year since last menstrual cycle) or permanently sterilized (eg, tubal occlusion, hysterectomy, bilateral salpingectomy) may be considered as not of reproductive potential.

Treatment with MT-3724 may proceed only if the pregnancy test is documented as negative at the most recent assessment. See [Section 8.5.3.2](#) for the guidance about reporting the onset of pregnancy during the study.

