### 2.2.1 Summary of Clinical Experience

The clinical development program for MT-3724 is being evaluated in 3 ongoing studies: 1 monotherapy study (MT-3724\_NHL\_001 [NHL\_001]) and 2 combination therapy studies (MT-3724\_NHL\_002 [NHL\_002] and MT-3724\_NHL\_003 [NHL\_003]) with gemcitabine and oxaliplatin (GEMOX) and lenalidomide (LEN), respectively. Further studies of MT-3724 in other subtypes of NHL are planned.

Data from the MT-3724 monotherapy study, NHL\_001, showed clinical antitumor activity in heavily pre-treated subjects with relapsed or refractory DLBCL who had low serum level of rituximab before the start of treatment.

Across 3 studies (NHL\_001, NHL\_002 and NHL\_003) as of 28 August 2020, capillary leak syndrome (CLS) has been reported in 5 subjects: 2 subjects from NHL\_001 dosed at 75  $\mu$ g/kg/dose, 2 subjects from NHL\_002 dosed at 10  $\mu$ g/kg/dose, and 1 subject from NHL\_003 dosed at 25  $\mu$ g/kg/dose. The maximum severity for all events was Grade 2. After the data cutoff, 1 event of Grade 5 CLS was reported in the NHL\_001 study, Part 3 dosed at 50  $\mu$ g/kg/dose. As a

result, more stringent safety measures are implemented in all MT-3724 trials including this protocol version.

Important identified risks for MT-3724 include infections (including pneumonia and viral infections), CLS, Neutropenia, and Edema and Peripheral Edema. Important potential risks include acute kidney injury, Myalgia/muscle weakness, systemic inflammatory response syndrome (SIRS)/ cytokine release syndrome (CRS), Infusion related reactions, Tumor lysis syndrome, and Reproductive risk.

Adverse events of special interest include Neutropenia, acute kidney injury, CLS, SIRS/CRS.

Please refer to the Investigator's Brochure for comprehensive information available for MT-3724 to date.

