## 5.1 Inclusion Criteria

Subjects meeting ALL of the following inclusion criteria will be eligible for participation of the study:

1. Subjects must be informed about the study and fully consent to participation as demonstrated by signing the written ICF before any screening procedure.
2. Male and female subjects  $\geq 18$  years of age at the time of informed consent
3. Subjects must have relapsed or refractory DLBCL according to the Revised European American Lymphoma/World Health Organization classification ([Swerdlow, 2016](#)). Subjects must have proof of CD20+ DLBCL, based on either:
  - a. historical biopsies (obtained with diagnosis of relapsed or refractory disease), or
  - b. fresh biopsies
  - c. bone marrow biopsy, excisional lymph node biopsy, and core biopsy of any involved organ are all acceptable methods; Fine Needle Aspirate is not acceptable.

NOTE: Composite lymphoma (DLBCL and indolent histology in the same specimen) is also acceptable.
4. Subjects must have received at least 2 SoC regimens (including anti-CD20 antibody therapy) appropriate for DLBCL treatment.
  - a. Subjects whose prior therapy includes CAR-T-cell therapy are eligible
  - b. Subjects who underwent stem cell transplant (SCT)  $> 100$  days for autologous SCT or  $> 180$  days for allogeneic SCT before study drug administration.
  - c. Subjects who have been ineligible for SoC DLBCL treatment(s) may be eligible at the investigator's discretion, upon sponsor approval.
5. Subjects must have at least 1 bi-dimensional tumor lesion at screening that is measurable by CT and/or magnetic resonance imaging (MRI) according to the Lugano criteria ([Cheson, 2014](#)). Bi-dimensionally measurable tumor lesion by CT and/or MRI is defined as longest diameter of  $> 1.5$  cm for lymph nodes and  $> 1.0$  cm for extranodal disease.
6. Subjects must have life expectancy of  $> 3$  months from the start of treatment.
7. Subjects must have ECOG performance status of 0-2.
8. Subjects must have met ALL the following laboratory criteria:
  - a. absolute neutrophil count (ANC)  $\geq 1.0 \times 10^9/L$  with no myeloid growth factors (granulocyte colony-stimulating factor [G-CSF] or granulocyte-macrophage colony-stimulating factor preparations) administered within 2 weeks of C1D1
  - b. platelet count  $\geq 50 \times 10^9/L$  with no Thrombopoietin-receptor agonists agents or platelet transfusions given within 2 weeks of C1D1

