- c. hemoglobin  $\geq 8.0$  g/dL with no erythropoietin stimulating agents or peripheral red blood cell (PRBC) transfusions within 2 weeks of C1D1
- d. creatinine clearance (CLcr) to be  $\geq 50$  ml/min either measured or estimated using the Cockcroft-Gault formula ([Section 10.2.2.2](#)).
- e. total bilirubin (or direct bilirubin for patients with Gilbert's disease)  $< 1.5 \times$  upper limit of normal (ULN)
- f. alanine transaminase (ALT)  $\leq 3.0 \times$  ULN (or  $\leq 5.0 \times$  ULN if liver involvement).
- g. aspartate aminotransferase (AST)  $\leq 3.0 \times$  ULN (or  $\leq 5.0 \times$  ULN if liver involvement).
- h. international normalized ratio (INR) or prothrombin time (PT)  $\leq 1.5 \times$  ULN (unless on therapeutic anticoagulants)
- i. Activated partial thromboplastin time  $\leq 1.5 \times$  ULN (unless on therapeutic anticoagulants)

9. Have adequate serum albumin, as determined by:

- a. albumin  $\geq 3.0$  g/dL

10. QT interval correction for heart rate using Fridericia's formula (QTcF)  $\leq 480$  ms determined as the average of 3 QTcF values from the triplicate ECG obtained at screening.

11. Women of reproductive potential must have a negative highly sensitive pregnancy test within 72 hours before the start of treatment. Women who are postmenopausal or permanently sterilized (eg, tubal occlusion, hysterectomy, bilateral salpingectomy) may be considered as not of reproductive potential.

12. Subjects of reproductive potential must agree either to abstain continuously from heterosexual intercourse or to use a highly effective birth control method from signing the informed consent until the STFU visit for females and until 90 days after the last dose of MT-3724 for males. Refer to [Section 10.4](#) for guidance on contraception.

13. Subject must be able to comply with all study-related procedures and medication use.

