## 10.4 Appendix 4: Contraceptive Guidance and Collection of Pregnancy Information

### Definitions:

#### Woman of Childbearing Potential (WOCBP)

A woman is considered fertile following menarche and until becoming postmenopausal unless permanently sterile (see below).

If fertility is unclear (eg, amenorrhea in adolescents or athletes) and a menstrual cycle cannot be confirmed before first dose of study intervention, additional evaluation should be considered.

Women in the following categories are not considered WOCBP:

1. Premenarchal
2. Premenopausal female with 1 of the following:
  - Documented hysterectomy
  - Documented bilateral salpingectomy
  - Documented bilateral oophorectomy

For individuals with permanent infertility due to an alternate medical cause other than the above, (eg, mullerian agenesis, androgen insensitivity), investigator discretion should be applied to determining study entry.

Note: Documentation can come from the site personnel's: review of the subject's medical records, medical examination, or medical history interview.

3. Postmenopausal female
  - A postmenopausal state is defined as no menses for 12 months without an alternative medical cause.
  - A high follicle-stimulating hormone (FSH) level in the postmenopausal range may be used to confirm a postmenopausal state in women not using hormonal contraception or hormonal replacement therapy (HRT). However, in the absence of 12 months of amenorrhea, confirmation with more than 1 FSH measurement is required.
  - Females on HRT and whose menopausal status is in doubt will be required to use 1 of the non-estrogen hormonal highly effective contraception methods if they wish to continue their HRT during the study. Otherwise, they must discontinue HRT to allow confirmation of postmenopausal status before study enrollment.

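### Section 10.2.2.1 decides who needs a pregnancy test with a looser rule than Appendix 4: menopause by elapsed time alone, and tubal occlusion counted as permanent sterilization

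*Protocol*

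**What the plan says.** Three places in the protocol bear on who is tested.

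- **Section 10.2.2.1 (Pregnancy Test)** applies the test only to women of childbearing potential. It then says which women may be treated as outside that group: "Women who are postmenopausal (> 1 year since last menstrual cycle) or permanently sterilized (eg, tubal occlusion, hysterectomy, bilateral salpingectomy". It also makes the test a gate for dosing: "Treatment with MT-3724 may proceed only if the pregnancy test is documented as negative at the most recent assessment".
- **Inclusion criterion 11 (synopsis and Section 5.1)** requires a negative test within 72 hours before treatment starts. It exempts postmenopausal women without defining the term, and it exempts women who are "permanently sterilized (eg, tubal occlusion, hysterectomy, bilateral salpingectomy) may be considered as not of reproductive potential".
- **Appendix 4 (Section 10.4)** takes a woman as fertile from menarche until she is postmenopausal or permanently sterile. On the first, "A postmenopausal state is defined as no menses for 12 months without an alternative medical cause". For premenopausal women its surgical categories are hysterectomy, bilateral salpingectomy and bilateral oophorectomy. Bilateral tubal occlusion appears only later, among the highly effective contraceptive methods.

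Appendix 4 also covers doubtful cases. Where fertility is unclear and "a menstrual cycle cannot be confirmed before first dose of study intervention, additional evaluation should be considered". For permanent infertility from another medical cause, "investigator discretion should be applied to determining study entry".

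Section 2.2.1 names reproductive risk among the important potential risks of MT-3724: "Infusion related reactions, Tumor lysis syndrome, and Reproductive risk".

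**The concern.** The same protocol holds two definitions of the women who need no test, and the looser one is where staff are sent. In Table 10-1 the β-HCG entry carries a footnote pointing to Section 10.2.2, and the local-laboratory pregnancy test is listed as done where applicable. Section 10.2.2.1 is the text that settles applicability. Neither it nor criterion 11 refers directly to Section 10.4. Criterion 12 does, but for contraception.

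What is at stake is subject safety. Pregnancy is an exclusion (criterion 16), a positive test requires withdrawal (Section 7.1), and dosing depends on the most recent test being negative. The withdrawal rule and the dosing gate work only if a test is done. For a woman exempted under 10.2.2.1 they do not operate, at entry or at any later Day 1.

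**Working it through.** This is a comparison of texts. The plan gives no figure to reproduce.

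**Step 1. The rules side by side.**

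| Element | Section 10.2.2.1 | Criterion 11 | Appendix 4 |
|---|---|---|---|
| Postmenopausal: time | More than 1 year since last cycle | Not defined | 12 months without menses |
| Postmenopausal: cause | No condition | Not defined | No other medical cause |
| Tubal occlusion | Permanent sterilization | Permanent sterilization | Not among the non-childbearing categories; a contraceptive method |
| Direct reference to 10.4 | None | None | Not applicable |

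The difference between more than 1 year and 12 months is immaterial. The missing condition on cause and the placing of tubal occlusion are what matter.

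**Step 2. Two cases.**

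- *A woman with 14 months of amenorrhea from another medical cause, not permanently sterile.* On the parenthetical in 10.2.2.1 a site may treat her as outside the tested group. Under Appendix 4 she is not postmenopausal on that ground, so she remains of childbearing potential and is tested.
- *A premenopausal, menstruating woman with bilateral tubal occlusion.* Under 10.2.2.1 and criterion 11 she may go untested. Under Appendix 4 she is in none of the listed non-childbearing categories and is a woman using a highly effective method.

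Each woman gets a different answer depending on which section the site opens.

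**Step 3. Size for one exempted woman.** Table 1-1 places the test within 72 hours before Day 1 of the cycle, and again at EoT and STFU. Table 6-1 gives 6 infusions in each of Cycles 1 and 2, and 3 in each later cycle.

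- Gating tests omitted over k cycles = k: 2 over 2 cycles, 6 over 6 cycles.
- Infusions given in that time: 6 + 6 = 12 over 2 cycles; 12 + 4 × 3 = 24 over 6 cycles.
- Tests omitted that do not gate dosing: up to 2 (EoT and STFU). These may be missed anyway when those visits are by telephone (Sections 8.1.3 and 8.1.4).

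The infusion counts restate the dosing schedule for any subject treated that long. They describe how much dosing the gate would have covered. They do not measure pregnancy risk.

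**Step 4. Number of women.** The documents give no distribution of sex, age or menstrual status, so no number can be derived.

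**The case against.** A reader might infer that 10.2.2.1 exempts amenorrhea whatever its cause, or tells sites not to test. The documents do not support that. The section is silent on cause, says only that such women may be regarded as not of reproductive potential, and exempts women who are postmenopausal, with the time given as a gloss. It also opens with the term childbearing potential, which Appendix 4 defines. A site reading the two together would test the woman in the first case. There is an indirect route as well: 10.2.2.1 points to Section 8.5.3.2, which cites Section 10.4, though for contraception.

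A reader might also infer that these women are dosed with no protection. That too goes beyond the text. Criterion 12 requires abstinence or highly effective contraception and does refer to Section 10.4, where such methods are credited with a failure rate below 1% per year when used properly. A woman with tubal occlusion already has one of the listed methods. The medical monitor reviews all screening data (Section 5), and investigators may order extra tests (Section 10.2.1).

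Finally, the affected group is not shown to exist. The amenorrhea example in Appendix 4 concerns adolescents and athletes, a poor fit for adults under criterion 4: "Subjects must have received at least 2 SoC regimens (including anti-CD20 antibody therapy) appropriate for DLBCL treatment". That such treatment, or a prior transplant, can stop menses is a clinical assumption which the documents do not state.

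All of this stands as mitigation and keeps the severity low. It does not remove the conflict. Criterion 12 protects the woman only if the site classifies her by Section 10.4 there. Monitor review does not say which definition governs, and the extra evaluation in Appendix 4 is advice that does not order a pregnancy test.

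**Conclusion.** The inconsistency is real and confined to wording. Section 10.2.2.1 defines menopause for testing by time alone, and with criterion 11 it treats tubal occlusion as permanent sterilization. Appendix 4 does neither. A site following 10.2.2.1 could therefore omit the gating test in a woman whom Appendix 4 counts as of childbearing potential, at the rate of one test per cycle.

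The conclusion rests on the texts alone. It assumes only that a site may use 10.2.2.1 without consulting Appendix 4, which the footnote in Table 10-1 makes plausible. No claim is made about how many women are affected, and none would be consistent with everything in the documents.

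This is a low-severity subject-safety point and a cheap improvement. It has no effect on endpoints, sample size, DLT decisions or analysis.

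**What to change.** Align the exemption with Appendix 4 at three places:

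1. **Section 10.2.2.1:** replace the time-only parenthetical with the Appendix 4 definition (12 months without menses and no other medical cause), add a reference to Section 10.4, and delete tubal occlusion from the examples.
2. **Criterion 11 in the synopsis:** delete tubal occlusion and add a reference to Section 10.4.
3. **Criterion 11 in Section 5.1:** the same edit.

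Keep the term reproductive potential in criterion 11. Criterion 12 uses it, and changing one without the other would create a new mismatch.

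Women with amenorrhea from another medical cause, and women with tubal occlusion, would then be tested by default. Permanent infertility from another medical cause would stay at the investigator's discretion under Appendix 4.

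The cost is a wording change in an amendment. Each woman newly tested has one extra test per cycle and up to 2 more at EoT and STFU, all at visits already scheduled.
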